11.2.2. Sensitivity of Sample Size to Assumptions

Table 5 displays the power of the Z test for different 22-day response proportions. In the power calculations, we have assumed that the absolute difference in true clinical response proportions is 0.20. If the effect size is larger than anticipated, power will be greater. If the effect size is less than 50%, power will be much lower. For example, if the true clinical response proportions are 0.20 and 0.30, power for the Z test drops to 37%. This situation could arise if the case definition of coccidioidomycosis pneumonia has lower specificity than expected. That is, per the protocol definition, some subjects who do not have coccidioidomycosis pneumonia are erroneously classified as cases.

This misclassification could result in an attenuated treatment effect. As displayed in Table 5, depending on the magnitude of the effect attenuation, power can be greatly affected.

Table 5: Power of the Z Test for Different Day 22 Response Rates

		Rate in Fluconazole Arm								
		0.1	0.2	0.3	0.4	0.5	0.6	0.7	0.8	0.9
Rate in Placebo Arm	0.1	5.0	50.8	94.8	100	100				
	0.2		5.0	37.1	87.6	99.6	100			
	0.3			5.0	31.6	82.8	99.2	100		
	0.4				5.0	29.4	81.2	99.2	100	
	0.5					5.0	29.4	82.8	99.6	100
	0.6						5.0	31.6	87.6	100
	0.7							5.0	37.1	94.8
	0.8								5.0	50.8
	0.9									5.0

In the power calculations, we have assumed that the clinical response proportion in the placebo arm is 0.20. If the effect size is maintained at 0.20, but the proportions are nearer to 0.50, power will be lower than reported, and if the proportions are farther from 0.50, power will be higher than reported. This is a result of the fact that the variance of a binomial distribution with probability of response p is given by $p*(1-p)$ which is maximized at $p = 0.50$.

The misclassification of coccidioidomycosis pneumonia described above could result in an attenuated treatment effect and/or attenuated arm-specific response proportions. The difficulty in predicting the magnitude of the misclassification or its effect on the power available for analyses highlights the importance of the alternate case definition analyses (Exploratory Objective 5). The primary analysis will be performed in the cocci-positive per-protocol population which excludes subjects who do not meet the primary case definition of coccidioidomycosis pneumonia. As denoted in Section 11.2.3 below, we estimate that a subset of the enrolled

population will be eligible for the cocci-positive per-protocol population. If the primary case definition does not adequately capture all subjects who truly have coccidioidomycosis pneumonia (i.e. has a high false-negative rate), two consequences are possible. First, the observed proportion of enrolled subjects that are eligible for the cocci-positive per-protocol population may be higher than our estimate. This possibility prompted the planned sample size assessment described in Section 11.3.3. Second, since a subset of all enrolled cocci-positive subjects would be included in the primary analysis, the observed treatment effect may be altered from the true treatment effect if the cocci-positive subjects who meet the primary case definition differ in any meaningful way from those cocci-positive subjects who do not meet the primary case definition. Again, this highlights the importance of the planned secondary analyses. The power calculations in this section were performed with PROC POWER in SAS 9.4.

11.2.3. Calculation of Target Enrollment

We estimate that 20% of the enrolled population will be eligible for the cocci-positive per protocol analysis population. Therefore, to reach the cocci-positive per protocol analysis population sample size of 200 subjects, it will be necessary to enroll at least 1,000 subjects to the study.

Since the assumptions underlying the sample size calculations are uncertain, a blinded re-assessment of sample size and target enrollment will be performed at an interim analysis while enrollment is ongoing. Refer to the next section on Planned Interim Analyses for a discussion.

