11.2. Sample Size Considerations

11.2.1. Sample Size for Per Protocol Analysis Population

The primary analysis will compare the proportion of subjects achieving clinical response at Day 22 among efficacy evaluable subjects, defined as subjects in the Cocci-Positive Per Protocol analysis population who meet the case definition of coccidioidomycosis pneumonia who were compliant with the intervention administration and have coccidioidal serology data available at the Day 1 and 22 visits. We further assume that the clinical response proportion at Day 22 will be 0.20 in the placebo arm, and 0.40 in the fluconazole arm. As described in section 11.2.3, enrollment will continue until 200 subjects are evaluable for efficacy, 100 in each treatment arm, which suffices for 88% power for the Z test with unpooled variance to compare proportion of clinical responses at Day 22 at the two-sided level of 0.05. This is the primary sample size calculation which forms the basis for target enrollment to the study and for subsequent sample size re-estimation procedures at scheduled interim analyses while the study is enrolling.

A secondary analysis in the Cocci Positive Modified Intent-to-Treat population will compare the proportion of responders at Day 22, treating subjects dropping out before the Day 22 visit as non-responders. Assuming that the probability of drop-out before Day 22 is 20% among cocci-positive subjects, we would expect that 250 cocci-positive subjects would be available for this secondary analysis as a result of reaching the target sample size of 200 cocci-positive subjects with Day 22 follow-up for the primary analysis. Since subjects who drop-out are considered non-responders, the probability of response in the control-arm subjects would be $0.8 * 0.2 = 0.16$, and in the treated subjects would be $0.8 * 0.4 = 0.32$. The Z-test with unpooled variance has power of 85% to detect this difference in response proportions with 125 cocci-positive subjects per arm.

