A secondary analysis in the Intent-to-Treat population will compare the proportion of responders at Day 22 between fluconazole and control arms in all randomized subjects, using a two-sided level .05 test of non-inferiority with a margin of an absolute difference of 0.05. Subjects who drop-out before Day 22 will be imputed as non-responders for cocci-positive subjects, and as responders for cocci-negative subjects. Assuming that an enrolled subject has a 20% chance of being cocci-positive, and that the probability of response is 20% among cocci-positive subjects receiving control, 40% for cocci-positive subjects receiving treatment, and 70% for cocci-negative subjects, then the probability that a control subject responds is given by $0.2*(0.8*0.2 + 0.2*0.0) + 0.8*(0.8*0.7 + 0.2*1.0) = 0.64$, and the probability that a treated subject responds is given by $0.2*(0.8*0.4 + 0.2*0.0) + 0.8*(0.8*0.7 + 0.2*1.0) = 0.672$. The non-inferiority test has power of 78% if 1,000 subjects are enrolled, and 86% if 1,250 subjects are enrolled.

The power calculations in this section were performed with PROC POWER in SAS 9.4 or in R.

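### Section 11.2 uses 20% for two different shares, cocci-positive and per-protocol-eligible, so its stated powers do not rest on one set of inputs at 1,000 enrolled

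*Combined protocol and SAP*

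**What the plan says.** Section 11.2.1 sizes the trial on the cocci-positive PP population: "enrollment will continue until 200 subjects are evaluable for efficacy, 100 in each treatment arm", for 88% power at 0.20 versus 0.40. It adds: "This is the primary sample size calculation which forms the basis for target enrollment to the study". Section 11.2.3 turns 200 into 1,000 with a single share: "We estimate that 20% of the enrolled population will be eligible for the cocci-positive per protocol analysis population".

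For the cocci-positive mITT analysis, section 11.2.1 works back from 200 to a larger group. "Assuming that the probability of drop-out before Day 22 is 20% among cocci-positive subjects", the text says, "we would expect that 250 cocci-positive subjects would be available for this secondary analysis" as a consequence of "reaching the target sample size of 200 cocci-positive subjects with Day 22 follow-up for the primary analysis". The stated power is 85% with 125 per arm.

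For the ITT non-inferiority analysis, the same section starts from a different share: "Assuming that an enrolled subject has a 20% chance of being cocci-positive". It applies 20% drop-out within that group and within the cocci-negative group, obtains response rates of 0.64 and 0.672, and concludes: "The non-inferiority test has power of 78% if 1,000 subjects are enrolled, and 86% if 1,250 subjects are enrolled".

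Section 11.4.1 makes the cocci-positive PP population a subset of the cocci-positive subjects. Members must also be compliant and have serology at Days 1 and 22.

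**The concern.** The PP population is what remains of the cocci-positive subjects after losses. The two shares can both be 20% only if no cocci-positive subject is lost, yet section 11.2.1 assumes that 20% of them drop out before Day 22. The mITT paragraph shows the gap, because 250 cocci-positive subjects out of 1,000 enrolled is 25%, not 20%.

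A reader of section 11.2 would take 88%, 85% and 78% as the powers of one trial of 1,000. They are not. Either the non-inferiority power belongs to a different case mix from the one behind the target, or 1,000 is not expected to deliver 200 evaluable subjects. The second would matter more, because the interim feasibility reviews judge whether the planning assumptions are adequate, and those assumptions should be stated consistently.

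**Working it through.** **Inputs, all from sections 11.2.1 and 11.2.3.** Drop-out before Day 22 is 20%. Response is 0.20 (cocci-positive control), 0.40 (cocci-positive treated) and 0.70 (cocci-negative). Drop-outs count as non-responders if cocci-positive and as responders if cocci-negative. The margin is 0.05 and the test is two-sided at 0.05. Allocation is 1:1 (section 5.3.1). Let q be the cocci-positive share of enrolled subjects.

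**Formulas.** ITT response in an arm = q × 0.8r + (1 − q) × (0.8 × 0.7 + 0.2), with r = 0.2 or 0.4. Non-inferiority power = Φ((0.05 + pT − pC)/SE − 1.96), with SE = √[(pC(1 − pC) + pT(1 − pT))/n] and n per arm. Superiority power is the same without the margin.

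**Step 1: reproduce the plan (q = 0.20).**
- pC = 0.2 × 0.16 + 0.8 × 0.76 = 0.640; pT = 0.2 × 0.32 + 0.8 × 0.76 = 0.672.
- n = 500: SE = √(0.450816/500) = 0.0300; 0.082/0.0300 − 1.96 = 0.771; power 78.0%.
- n = 625: SE = 0.0269; power 86.3%.

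Both printed figures are reproduced, so the method matches the plan's.

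**Step 2: the shares.**
- Non-inferiority basis: 0.20 × 0.80 = 16% of enrolled subjects are cocci-positive with Day 22 follow-up. The PP share is at most that.
- Target basis: 200/1,000 = 20% PP. With 20% drop-out, 200/0.80 = 250 positive, and 250/1,000 = 25%.

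**Step 3: non-inferiority power on the target's basis (q = 0.25).**
- pC = 0.25 × 0.16 + 0.75 × 0.76 = 0.610; pT = 0.25 × 0.32 + 0.75 × 0.76 = 0.650.
- n = 500: SE = √(0.4654/500) = 0.0305; 0.09/0.0305 − 1.96 = 0.990; power 83.9%.
- n = 625: power 91.0%.

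**Step 4: the other powers on each basis.**
- Primary, 0.20 versus 0.40, 100 per arm: 88.5% with unpooled variance and 87.6% with pooled variance. The latter is the figure in Table 5, and the stated 88% stands.
- Primary, 80 per arm: 80.7% unpooled (79.4% pooled).
- mITT, 0.16 versus 0.32, 125 per arm: 85.4%; 100 per arm: 76.9%.
- Enrolment needed for 200 PP at q = 0.20: 200/(0.20 × 0.80) = 1,250.

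| | 25% positive, 1,000 enrolled | 20% positive, 1,000 enrolled | 20% positive, 1,250 enrolled |
|---|---|---|---|
| Cocci-positive | 250 | 200 | 250 |
| PP (drop-out the only loss) | 200 | 160 | 200 |
| Primary power | 88% | about 81% | 88% |
| mITT power | 85% | about 77% | 85% |
| Non-inferiority power | about 84% | 78% | 86% |

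No column contains the stated combination of 88%, 85% and 78%. All powers are for a fixed sample, before the futility looks.

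**The case against.** The best defence is that nothing is miscalculated and the design adapts.

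- A reader might infer that 78% is an error and 84% the correct value. The documents do not support that. The 78% follows exactly from the inputs stated beside it, and 84% holds only if the target's basis is the intended one.
- The figure for 1,250 is already printed. At 20% positivity, 1,250 enrolled gives exactly 250 cocci-positive and 200 evaluable subjects, so 88%, 85% and 86% agree there. This stands, but the text never links 1,250 to reaching 200 evaluable subjects.
- Sections 11.2.2, 11.2.3 and 11.3.3 acknowledge uncertainty in the assumptions. Table 10 simulates a PP share of 10%, lower than the 16% derived here. This stands too, although the base scenarios of Table 10 keep the 20% PP share.
- A reader might infer that the blinded re-estimation inherits the disputed 20%. It does not. Section 11.3.3 predicts the evaluable count from accrued data, and only the simulation scenarios use a fixed share.
- If positivity is 25%, the printed non-inferiority powers are conservative.

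These arguments limit the consequences. None of them reconciles the two shares.

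**Conclusion.** The inconsistency holds, and it is minor. The non-inferiority paragraph assumes 20% positivity, while the 1,000 target, read with the 200-to-250 step, implies 25%. The effect is either about 6 percentage points of understated non-inferiority power at 1,000 (83.9% against 78.0%), or a planned total about 250 below what 200 evaluable subjects require.

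The documents do not settle which share is meant. A reader might take the facility data in section 2.1 (178 of 896 tested, 20%) as support for 20% positivity. Those data cover only the 18% of pneumonia cases known to be tested, and positivity varied from 7% to 45% by facility. They also come from routine testing, not from the trial's serial case definition. The same section quotes 15% to 29%, which covers both readings.

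Nor do the documents support the inference that the primary analysis will be underpowered. Enrolment continues until 200 are evaluable, and section 11.3.3 raises the target if fewer are predicted. The 81% would apply only if enrolment stopped at 1,000 with 20% positivity.

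The figures assume the plan's response rates and imputation, and drop-out as the only loss from cocci-positive to PP. The documents give no non-adherence rate; any such loss would lower the PP yield.

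**What to change.** In section 11.2, state the cocci-positive share and the loss from cocci-positive to PP (drop-out plus non-adherence) as separate inputs, and use that one set for every power and for the target.

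- If positivity is 25%: keep 1,000 and restate the non-inferiority power as about 84% at 1,000 and 91% at 1,250. Two figures in one sentence change and the sample size does not.
- If positivity is 20%: say that 1,000 enrolled is expected to yield about 160 PP subjects, and that the 200-evaluable target with its 88%, 85% and 86% powers corresponds to about 1,250 enrolled, before any non-adherence loss. The cost is disclosing a planning total 250 higher. The implied 16% PP share lies between the two shares already simulated for Table 10.

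Either way the change is to the text of sections 11.2.1 and 11.2.3. The primary hypothesis, the test and the rule of enrolling until 200 are evaluable are unaffected.

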11.3. Planned Interim Analyses

The following [Table 6](#) shows the planned schedule of DSMB review of the data. The DSMB will meet at minimum once per year and schedule ad hoc reviews as needed.

Table 6: Planned Interim Analysis Table

Analysis	Enrollment Target	Purpose of the Analyses
Interim 1	250	Safety Review and Enrollment Feasibility
Interim 2	500	Safety Review, Futility, and Enrollment Feasibility
Interim 3	750	Safety Review, Futility, and Enrollment Feasibility

Final DSMB review	1,000 6-8 months after data lock	Unblinded comprehensive review of cumulative safety and efficacy data for the study.
-------------------	--	--

11.3.1. Interim Safety Review

Interim safety review may include enrollment and demographic information, medical history, concomitant medications, physical assessments, clinical laboratory values, dosing, and SAEs as defined in Section 9.2.2. Additional data may be requested by the DSMB, and interim statistical reports may be generated as deemed necessary and appropriate by DMID. The DSMB may receive data in aggregate and presented by group. The DSMB may also be provided with expected and observed rates of the expected AEs in an unblinded fashion. The DSMB will meet and review this data at scheduled time points or ad hoc as needed during the study as defined in the DSMB charter. As an outcome of each review/meeting, the DSMB will make a recommendation to DMID as to the advisability of proceeding with study enrollment and procedures (as applicable), and to continue, modify, or terminate the study.

Additionally, the study will be monitored to determine if any of the halting rules described in Section 9.5 are met.

11.3.2. Interim Immunogenicity or Efficacy Review

At the second and third interim analysis, the unblinded statistical team will calculate the probability conditional on the current trend in the accumulated data that the final analysis will show a benefit in favor of fluconazole. The DSMB will report to the sponsor only that the trial met the standard for continuation (conditional power above 5%). The sponsor will weigh the recommendation of the DSMB regarding futility and the separate blinded assessment of enrollment feasibility, and will decide whether to continue the trial, and if so, whether to increase the sample size, and by how much. It is recognized that statistical futility (low conditional power), and operational futility (unachievable enrollment targets), are closely related issues, and that this somewhat arbitrary distinction is being made to facilitate blinded decision making. The power calculations in Section 11.2.1 considered the power of the Z test for a fixed sample size and no interim analysis. A simulation study was performed to calculate the power available for the final analysis in a trial containing a futility analysis to be performed after 500 and 750 subjects have been enrolled and followed until Day 22. In this setting, uniform enrollment was also assumed.

At each futility analysis, the conditional power was calculated and if the conditional power was less than 5%, the trial was terminated. [Table 7](#) displays the power of the Z test for different Day 22 response rates resulting from the simulation study. Comparing these results with [Table 5](#) in

Section 11.2.2., there is minimal impact on power. If the true clinical response proportions are 0.20 and 0.40, the power drops slightly to 85.9%.

Table 7: Power of the Z Test for Different Day 22 Response Rates with a Futility Analysis

		Rate in Fluconazole Arm								
		0.1	0.2	0.3	0.4	0.5	0.6	0.7	0.8	0.9
Rate in Placebo Arm	0.1	4.8	48.7	93.9	99.8	100.0				
	0.2		4.7	34.9	85.9	99.1	100.0			
	0.3			4.7	30.1	80.8	98.6	100.0		
	0.4				5.0	27.7	78.7	98.6	100.0	
	0.5					4.8	28.0	80.5	99.1	100.0
	0.6						5.0	29.6	85.6	99.9
	0.7							4.7	34.8	94.0
	0.8								4.7	49.2
	0.9									4.8

Table 8 and Table 9 display the chance of deeming the trial futile and terminating the trial at the second and third interim analysis, respectively. The selection of a 5% threshold for futility appears to be reasonable as, if the protocol assumptions are correct, the chance of deeming the trial futile at the second and third interim analysis is 4.5% and 2.2%, respectively. This results in a 6.7% chance of terminating the trial early due to futility. Given that the stopping rule is conservative, there is a high chance of terminating the trial early at either interim analysis when there is no treatment benefit (e.g. if the true rates in both arms are both 0.2, the chances of futility are 42.0% and 30.0%, or a 72.0% chance of terminating the trial early due to futility).

Table 8: Chance of Futility at Second Interim Analysis

		Rate in Fluconazole Arm								
		0.1	0.2	0.3	0.4	0.5	0.6	0.7	0.8	0.9
Rate in Placebo Arm	0.1	42.6	16.7	2.1	0.1	0.0				
	0.2		42.0	23.1	4.5	0.4	0.0			
	0.3			41.5	26.0	6.2	0.6	0.0		
	0.4				41.8	27.1	7.2	0.6	0.0	
	0.5					42.3	26.5	6.5	0.4	0.0
	0.6						41.8	25.8	4.8	0.1

	0.7							41.5	23.5	2.0
	0.8								42.0	17.6
	0.9									42.6

Table 9: Chance of Futility at Third Interim Analysis

		Rate in Fluconazole Arm								
		0.1	0.2	0.3	0.4	0.5	0.6	0.7	0.8	0.9
Rate in Placebo Arm	0.1	29.8	11.1	0.9	0.0	0.0				
	0.2		30.0	15.2	2.2	0.1	0.0			
	0.3			31.0	16.8	3.2	0.2	0.0		
	0.4				30.7	17.7	3.2	0.1	0.0	
	0.5					30.9	18.1	3.4	0.1	0.0
	0.6						30.7	17.5	2.4	0.0
	0.7							31.0	15.7	0.7
	0.8								30.0	10.0
	0.9									29.8

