11. STATISTICAL CONSIDERATIONS

11.1. Study Hypotheses

The primary objective of the study is to assess the clinical response of early empiric antifungal therapy with fluconazole at Day 22 in subjects with coccidioidomycosis pneumonia.

The study is designed to test the following hypothesis in the primary efficacy analysis conducted in the cocci-positive per protocol analysis population (see Section 11.4.1):

Null hypothesis: “The proportion of subjects with coccidioidomycosis pneumonia with protocol-defined clinical response is the same in the cohort of subjects receiving fluconazole as compared to placebo.”

Alternative hypothesis: “The proportion of subjects with coccidioidomycosis pneumonia with protocol-defined clinical response is different in the cohort of subjects receiving fluconazole as compared to placebo.”

The study design and primary hypothesis is based on the following parameters supplied by subject matter experts:

- The composite score will be sensitive to changes in the course of disease as a result of empiric treatment with fluconazole.
- A 50% reduction in composite score is a clinically meaningful reduction which has been used as a measure of clinical response in other trials.
- A Day 22 time point will be optimal for measuring clinical response as compared to a longer time point because subjects in both study arms will eventually resolve disease,
- The proportion of subjects responding at Day 22 will be 0.20 and 0.40 in the placebo and fluconazole arms, respectively.

However, there is considerable uncertainty in the design parameters, as they are based on natural history studies, and this is the first randomized trial of empiric therapy with fluconazole for coccidioidomycosis. The most important contribution of this trial may be to confirm or refute these assumptions and set the stage for future trials.

Several of the secondary and exploratory objectives in the trial are focused on validating the sensitivity of the composite score, and its individual components, to intervention with fluconazole. This is motivated by Blair et al. (2014) who reported that subjects who received antifungal treatment had a reduced time to full attendance at work and reduced time to 50% improvement in SF-36 Physical Component Score [13].

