Scenarios 1 and 4 correspond to the protocol specified alternative hypothesis in which the arm-specific Day 22 cumulative response is 0.40 and 0.20, and an assumed 20% of subjects are eligible for the per-protocol analysis. Comparing the adaptive design (Table 10) to the fixed sample size design (Table 5), there is little impact of adaption on either power or sample size. Scenarios 2 and 5 correspond to the protocol specified null hypothesis in which the arm-specific Day 22 cumulative response is 0.20 in both arms. In these scenarios, the type I error is preserved at < 5% and the average sample size is about 25% less than that of the fixed sample size of 1000. Scenarios 3 and 6 correspond to the protocol specified alternative hypothesis, but with only half as many subjects eligible for the per protocol analysis (10% versus 20%). In this setting power is increased from 56.9% without sample size re-estimation (not tabulated) to 69.8% or 64.4% corresponding to the limit of 1500 or 1250.

For comparison, if the arm-specific Day 22 cumulative response is 0.30 and 0.10 (attenuated response proportions with protocol-assumed effect size), and an assumed 20% of subjects are eligible for the cocci-positive per-protocol analysis, the power available is 94.7% (not displayed in Table 10). If the arm-specific Day 22 cumulative response is 0.35 and 0.20 (attenuated treatment effect), and an assumed 20% of subjects are eligible for the per-protocol analysis, the power available is 65.3% (not displayed in Table 10).

Table 10: Operating Characteristics of a Trial Design with Both a Futility and Sample Size Assessment at the Three Interim Analyses

Scenario	Power	Average Number of Subjects Enrolled	Average Accrual Goal
1, Fluconazole, Placebo Rates: 0.4, 0.2 Percentage of subjects eligible for cocci-positive PP: 20% Maximum Allowable Sample Size: 1500	87.1	1019	1046
2, Fluconazole, Placebo Rates: 0.2, 0.2 Percentage of subjects eligible for cocci-positive PP: 20% Maximum Allowable Sample Size: 1500	4.6	734	1026

3. Fluconazole, Placebo Rates: 0.4, 0.2 Percentage of subjects eligible for cocci-positive PP: 10% Maximum Allowable Sample Size: 1500	69.8	1336	1430
4. Fluconazole, Placebo Rates: 0.4, 0.2 Percentage of subjects eligible for cocci-positive PP: 20% Maximum Allowable Sample Size: 1250	87.0	1015	1044
5. Fluconazole, Placebo Rates: 0.2, 0.2 Percentage of subjects eligible for cocci-positive PP: 20% Maximum Allowable Sample Size: 1250	4.6	728	1025

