11.4.4.1. Primary Efficacy Analysis

The primary efficacy analysis tests the difference between the fluconazole and placebo treatment groups in the proportion of subjects with an occurrence of clinical response at Day 22. Subjects without a clinical response at Day 22 will be coded as treatment failures while subjects with a clinical response at Day 22 will be coded as an observed event if the clinical response outcome measure definition (Section 3.2.1) is met.

A test of difference between the proportion of clinical responses in the fluconazole and placebo groups at the Day 22 time point will be performed using the Z test. The use of this test statistic will permit us to use the method of B-values to calculate conditional power of the test in the planned futility analyses, as outlined in “Statistical Monitoring of Clinical Trials, a Unified Approach”, by Proschan et al [22]. Details of this procedure will be provided in the statistical analysis plan.

The primary efficacy analysis will be performed in the cocci-positive per protocol analysis population. Secondary analyses will be performed in the all randomized per protocol population, all randomized and cocci-positive ITT and the mITT populations (see also Secondary Objectives 1 and 6). Sensitivity analyses, which will assess the impact of drop-out, censoring mechanisms, and analysis methods on the primary analysis, may be performed. These analyses will be specified in the separate statistical analysis plan document.

In addition to the planned tests of hypotheses, descriptive analyses will be performed for the primary endpoint. The number of clinical responses observed will be tabulated by time point, including and beyond Day 22, and treatment group. Tabular and graphical summaries will be prepared for the composite MSG score across all assessment time points.

To investigate whether there is evidence of a differential diagnosis of coccidioidomycosis between treatment arms, which might result in selection bias for inclusion in our primary analysis, the number of coccidioidomycosis cases in each treatment arm will be compared among all randomized subjects.

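### The futility tables match a two-direction conditional power, not the stated rule of conditional power for a fluconazole benefit

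*Combined protocol and SAP*

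**What the plan says.** Section 11.3.2 sets the futility quantity for the second and third interim analyses: the unblinded statisticians are to "calculate the probability conditional on the current trend in the accumulated data that the final analysis will show a benefit in favor of fluconazole". After its review, the DSMB then tells the sponsor "only that the trial met the standard for continuation (conditional power above 5"%).

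The simulation in the same section is described without a direction: "if the conditional power was less than 5%, the trial was terminated". Section 11.4.4.1 says the Z test was chosen so that the team can "use the method of B-values to calculate conditional power of the test in the planned futility analyses", and leaves the details to a separate SAP.

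The final test is two-sided. Section 11.2.1 will "compare proportion of clinical responses at Day 22 at the two-sided level of 0.05", and the alternative hypothesis in 11.1 is that "clinical response is different in the cohort of subjects receiving fluconazole as compared to placebo".

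The results offered in support are:
- **Stopping, Tables 8 and 9:** "if the true rates in both arms are both 0.2, the chances of futility are 42.0% and 30.0%, or a 72.0% chance". At the design rates the chances are 4.5% and 2.2%, 6.7% in total.
- **Table 7:** null rejection of 4.7% to 5.0% along the diagonal, and 85.9% power at the design rates.
- **Section 11.3.3 and Table 10, null scenarios 2 and 5:** "the type I error is preserved at < 5"% (tabulated as 4.6%), with average enrolment of 734 or 728.

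**The concern.** A rule that stops when a fluconazole win looks unlikely must stop nearly every trial that trends toward placebo, and also those with only a weak trend toward fluconazole. With equal true rates, well over half of trials should therefore stop at the second interim. Every null cell in Table 8 lies between 41.5% and 42.6%. A null rejection rate close to 5% is equally out of place: it needs the placebo-favouring half of the two-sided rejections to survive the futility looks, and the stated rule removes that half.

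Two things are at stake. First, the protocol defends the 5% threshold with figures that belong to another rule. Second, the procedure is still to be detailed in the SAP, so the simulation code could be carried into the real interim analyses. A two-direction conditional power is high when fluconazole is clearly worse. The DSMB would then report that the continuation standard was met, and randomisation to the worse arm would go on. Tables 7 to 9 leave every cell with fluconazole below placebo blank, so a reader cannot see this.

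**Working it through.** **Inputs**
- Final test two-sided at 0.05, critical value 1.96 (11.2.1).
- 200 evaluable subjects, 100 per arm, being 20% of 1,000 enrolled (11.2.1, 11.2.3); allocation 1:1 (5.3.1).
- Futility looks at 500 and 750 enrolled (11.3.2), so information fractions t = 0.50 and 0.75.
- Current-trend conditional power by B-values (11.3.2, 11.4.4.1); stop below 5%.

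**Formulas.** With interim statistic Z, positive favouring fluconazole:
- Fluconazole benefit: CP_up = 1 − Φ((1.96 − Z/√t)/√(1−t))
- Placebo benefit: CP_low = Φ((−1.96 − Z/√t)/√(1−t))

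The stated rule stops if CP_up < 5%. A two-direction rule stops if CP_up + CP_low < 5%.

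**Closed form at the second interim.** Setting CP_up = 0.05 gives Z = √t × (1.96 − 1.645√(1−t)) = 0.7071 × (1.96 − 1.645 × 0.7071) = 0.563. With no treatment effect:
- Stated rule: P(Z < 0.563) = 71.3%
- Two-direction rule: P(|Z| < 0.563) = 42.7%, the lower tail adding almost nothing at that cut-off
- Table 8 at 0.2/0.2: 42.0%

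**Simulation.** Monte Carlo with 400,000 trials per scenario, random evaluable numbers at 20% of enrolment, unpooled Z, no sample size re-estimation. Paired stopping figures are second + third interim.

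| Fluconazole / placebo rate | Quantity | Protocol | Two-direction | Stated rule |
|---|---|---|---|---|
| 0.2 / 0.2 | Stopping | 42.0% + 30.0% | 42.0% + 30.0% | 71.2% + 14.9% |
| 0.2 / 0.2 | Rejection | 4.7% | 4.8% | 2.4% |
| 0.3 / 0.2 | Stopping | 23.1% + 15.2% | 23.1% + 15.2% | 27.4% + 11.6% |
| 0.4 / 0.2 | Stopping | 4.5% + 2.2% | 4.7% + 2.2% | 5.0% + 2.0% |
| 0.4 / 0.2 | Power | 85.9% | 85.9% | 85.9% |
| 0.2 / 0.4 | Stopping in total | not shown | 6.9% | essentially 100% |

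A pooled Z gives the same picture, with 2.2% to 2.3% null rejection under the stated rule. Other readings of conditional power do not fit the null row: design-effect conditional power gives 13.5% + 51.5%; null-drift gives 86.6% + 6.8% in one direction and 73.3% + 13.6% in two.

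**Average enrolment at 0.2/0.2.** Under the stated rule, without re-estimation: 0.712 × 500 + 0.149 × 750 + 0.139 × 1,000 ≈ 607, about 39% below 1,000. The two-direction rule gives about 714. Table 10, which includes re-estimation, shows 734 and 728, about 25% below 1,000. With re-estimation the stated rule gives roughly 615; that figure depends on how the re-estimation is coded and is less secure than the others.

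**When fluconazole is worse.** At half information with Z = −2, two-direction conditional power is 89%, while the probability of a fluconazole benefit is practically zero. At 0.2 on fluconazole and 0.4 on placebo, the two-direction rule takes 85.9% of trials to a significant result for placebo; the stated rule stops 99.7% at the second interim. At 0.10 and 0.20, early stopping is 28% (average enrolment 888) against 99.7% (average enrolment 507).

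**The case against.** The written rule is the safe one. As worded, 11.3.2 stops a trial trending toward harm, so continuing such a trial requires someone to program something other than the text. The SAP that would settle this is a separate document not available here. The DSMB can see data by group and recommend termination at any time. These points stand: the harm is conditional on which rule is coded. But DSMB discretion is not a rule, and the numerical halting criteria in 9.5 cover only liver and QT-related events.

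The case for the 5% threshold also survives. Early stopping at the design rates is 6.7% as stated and about 7.0% under the written rule, and stopping under no effect becomes more likely, not less. The statement that type I error stays below 5% is true under both rules, and the chance of falsely declaring a fluconazole benefit is the same under both. Off-diagonal power in Table 7 barely moves in the cells checked. All of this is correct. It confines the numerical error to the null and small-effect stopping chances, the null rejection rates and the null average enrolment.

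Finally, a two-direction conditional power is coherent with a two-sided test, so the text could instead be changed to match the simulation. That is logically possible. It would, however, abandon the stated purpose of asking whether a fluconazole benefit is still attainable, and would make continuing through a harmful trend the intended behaviour.

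**Conclusion.** The concern holds. The protocol states one futility rule and reports the operating characteristics of another. At rates 0.2/0.2 the stated rule gives about 86% early stopping rather than 72.0%, null rejection of about 2.2% to 2.4% rather than 4.7%, and average enrolment of about 607 without re-estimation, where Table 10 reports 734 and 728 with it. There is no type I error inflation and no material loss of power at the design rates.

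The protocol does not say that its simulation was two-directional; this is inferred. The inference is firm, because the two-direction rule matches the tabulated stopping chances closely, to the decimal in two rows, and none of the other definitions tried does. The results assume 20% evaluable, looks at half and three quarters of the information, and current-trend B-values, all as the protocol describes.

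**What to change.** In 11.3.2 and the SAP, define conditional power as P(final Z > 1.96 | current trend), with positive Z favouring fluconazole, and give the formula so that it cannot be programmed in two directions. Rerun Tables 7 to 10 under that definition. Replace the 42.0%, 30.0% and 72.0% figures (about 71%, 15% and 86%) and the tabulated null rejection rates (about 2.3%), and update the average enrolment for Table 10 scenarios 2 and 5 and the accompanying text. Fill in the cells where fluconazole is worse than placebo. Before the second interim, confirm that the program to be used implements the one-direction rule.

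The cost is one simulation rerun and revised tables: no added patients and no material loss of power.
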